4.2.3 Submitting Regulatory Documents

Submit required forms and documents to the CTSU Regulatory Office via the Regulatory Submission Portal on the CTSU website.

To access the Regulatory Submission Portal, log on to the CTSU members' website → Regulatory → Regulatory Submission.

Institutions with patients waiting that are unable to use the Regulatory Submission Portal should alert the CTSU Regulatory Office immediately at [name] in order to receive further instruction and support.

4.2.4 Checking Site Registration Status

You can verify your site's registration status on the members' side of the CTSU website.

- Log on to the CTSU members' website
- Click on *Regulatory* at the top of your screen
- Click on *Site Registration*
- Enter your 5-character CTEP Institution Code and click on Go

Note: The status shown only reflects institutional compliance with site registration requirements as outlined above. It does not reflect compliance with protocol requirements for individuals participating on the protocol or the enrolling investigator's status with the NCI or their affiliated networks.

4.3 Patient Registration

4.3.1 OPEN / IWRS

The Oncology Patient Enrollment Network (OPEN) is a web-based registration system available on a 24/7 basis. OPEN is integrated with CTSU regulatory and roster data and with the Lead Protocol Organization (LPOs) registration/randomization systems or Theradex Interactive Web Response System (IWRS) for retrieval of patient registration/randomization assignment. OPEN will populate the patient enrollment data in NCI's clinical data management system, Medidata Rave.

Requirements for OPEN access:

- A valid CTEP-IAM account.
- To perform enrollments or request slot reservations: Be on an LPO roster, ETCTN Corresponding roster, or Participating Organization roster with the role of Registrar. Registrars must hold a minimum of an AP registration type.
- If a DTL is required for the study, the registrar(s) must hold the OPEN Registrar task on the DTL for the site.
- Have an approved site registration for a protocol prior to patient enrollment.

To assign an Investigator (IVR) or Non-Physician Investigator (NPIVR) as the treating, crediting, consenting, drug shipment (IVR only), or receiving investigator for a patient transfer in OPEN, the IVR or NPIVR must list the IRB number used on the site's IRB approval on their Form FDA 1572 in RCR. If a DTL is required for the study, the IVR or NPIVR must be assigned the appropriate OPEN-related tasks on the DTL.

Prior to accessing OPEN, site staff should verify the following:

- Patient has met all eligibility criteria within the protocol stated timeframes, and
- All patients have signed an appropriate consent form and HIPAA authorization form (if applicable).

Note: The OPEN system will provide the site with a printable confirmation of registration and treatment information. Please print this confirmation for your records.

Access OPEN at <https://open.ctsu.org> or from the OPEN link on the CTSU members' website. Further instructional information is in the OPEN section of the CTSU website at <https://www.ctsu.org> or <https://open.ctsu.org>. For any additional questions, contact the CTSU Help Desk at [name] or [contact].

4.3.2 OPEN/IWRS Questions?

Further instructional information on OPEN is provided on the OPEN tab of the CTSU website at <https://www.ctsu.org> or at <https://open.ctsu.org>. For any additional questions contact the CTSU Help Desk at [name] or [contact]. Theradex has developed a Slot Reservations and Cohort Management User Guide, which is available on the Theradex website: <http://www.theradex.com/clinicalTechnologies/?National-Cancer-Institute-NCI-11>.

This link to the Theradex website is also on the CTSU website OPEN tab.

For questions about the use of IWRS for slot reservations, contact the Theradex Helpdesk at [contact] or Theradex main number [contact]; [contact].

4.4 **General Guidelines**

NCI Protocol #:10200
Version Date: 07/24/2020

Following registration, patients should begin protocol treatment as soon as possible. Issues that would cause treatment delays should be discussed with the Principal Investigator. If a patient does not receive protocol therapy following registration, the patient's registration on the study may be canceled. The Study Coordinator should be notified of cancellations as soon as possible.

5. BIOMARKER, CORRELATIVE, AND SPECIAL STUDIES

5.1 Biomarker Plan

Biomarker Name AND Lab PI and Site	Assay (CLIA: Y/N)	Use (Integral, Integrated, or Exploratory) AND Purpose	Tissue/Body Fluid Tested and Timing of Sample Collection	M/O	Use of NCI Resources (No / Pending Approval / Approved)	Funding Source(s)
11q23 rearrangement or partial tandem duplication [name] / Memorial Sloan-Kettering Cancer Center (MSKCC) Lab PI email:	Cytogenetics and FISH CLIA: Y BRC Review: No	Integral Evaluate eligibility	Bone marrow aspirate, peripheral blood Prior to enrollment and therapy cessation	M	ETCTN Tissue Bank: No CIMAC: No MoCha: No PADIS: No	CTEP CRADA
Myeloid mutational panel for NPM1 and no other targetable mutations [name] / Memorial Sloan-Kettering Cancer Center (MSKCC) Lab PI email:	Myeloid Mutations CLIA: Y BRC Review: No	Integral Evaluate eligibility	Bone marrow aspirate Prior to enrollment and therapy cessation	M	ETCTN Tissue Bank: No CIMAC: No MoCha: No PADIS: No	CTEP CRADA
Myeloid differentiation by Flow/FISH [name] / Memorial Sloan-Kettering Cancer Center (MSKCC) Lab PI email:	FACS, Flow cytometry, FISH CLIA: N BRC Review: Yes Submission Deadline:	Integrated Evaluate differentiation of cells with treatment	Bone marrow aspirate, peripheral blood End of cycle 1, end of cycle 3, and therapy cessation	M	ETCTN Tissue Bank: No CIMAC: No MoCha: No PADIS: No	CTEP CRADA
H3K79 ELISA [name] / Dana-Farber Cancer Institute (DFCI) Lab PI email:	H3K79 ELISA CLIA: N BRC Review: No	Integrated Quantitate methylation	Bone marrow aspirate Prior to enrollment, end of cycle 1, end of cycle 3, and therapy cessation	M	ETCTN Tissue Bank: No CIMAC: No MoCha: No PADIS: No	CTEP CRADA
qPCR for HOXA9 and Meis1 Expression [name] / Dana-Farber Cancer Institute (DFCI) Lab PI email:	qPCR CLIA: N BRC Review: No	Integrated Quantitate gene expression	Bone marrow aspirate Prior to enrollment, end of cycle 1, end of cycle 3, and therapy cessation	M	ETCTN Tissue Bank: No CIMAC: No MoCha: No PADIS: No	CTEP CRADA
MRD Negativity by Flow Cytometry [name] / Memorial Sloan-Kettering Cancer Center (MSKCC) Lab PI email:	Flow cytometry CLIA: Y BRC Review: No	Integrated Evaluate response to therapy	Bone marrow aspirate End of cycle 1, end of cycle 3, and therapy cessation	M	ETCTN Tissue Bank: No CIMAC: No MoCha: No PADIS: No	CTEP CRADA
Azacitidine PK profile [name] / Johns Hopkins Lab PI email:	LC-MS/MS CLIA: N GLP: Y BRC Review: No	Integrated Pharmacokinetic profile of azacitidine alone	Blood with THU to stabilize azacitidine C1D1 pre, and 0.25, 0.5, and 1 hr post	M	ETCTN Tissue Bank: No CIMAC: No MoCha: No PADIS: No	UM1 for sample processing; CTEP / NIH / foundation grants for PK assessment
Cell storage / DNA storage [name] / Memorial Sloan-Kettering Cancer Center (MSKCC) Lab PI email:	Cell storage / DNA storage CLIA: N BRC Review: No	Exploratory Evaluate valence of methylation in future	Bone marrow aspirate, nail clippings Prior to enrollment, end of cycle 1, end of cycle 3, and therapy cessation; nail clippings only prior to enrollment	M	ETCTN Tissue Bank: No CIMAC: No MoCha: No PADIS: No	CTEP CRADA

Biomarker Name AND Lab PI and Site	Assay (CLIA: Y/N)	Use (Integral, Integrated, or Exploratory) AND Purpose	Tissue/Body Fluid Tested and Timing of Sample Collection	M/O	Use of NCI Resources (No / Pending Approval / Approved)	Funding Source(s)
5-aza-2'-deoxycytidine Genomic Incorporation (from azacitidine) and DNA demethylation [name] / Johns Hopkins Lab PI email:	LC-MS/MS CLIA: N GLP: Y BRC Review: No	Exploratory Pharmacodynamic profile of azacitidine conversion to 5-aza-2'-deoxycytidine triphosphate and incorporation into DNA and its effect on DNA demethylation	PBMC and bone marrow aspirate PBMC: C1D8; Bone marrow aspirate: End of cycle 1, end of cycle 3, and therapy cessation	M	ETCTN Tissue Bank: No CIMAC: No MoCha: No PADIS: No	CTEP CRADA

The objective of the correlative studies is to better understand whether this combination is having the anticipated on-target effects and, if so, what the sequelae of those on-target effects may be.

Correlative studies will include morphology, flow cytometry, cytogenetics, and a myeloid genetics panel, all of which are standard of care. These will be performed on bone marrow biopsy samples taken at each time point - prior to therapy initiation and at the end of cycle 1 for the phase Ib, and prior to therapy initiation, end of cycle 1, end of cycle 3, end of cycle 6 and / or after therapy cessation for the phase II. Specimen collection for these assays will be mandatory. Integral biomarkers for identification of 11q23 / MLL rearrangements would be performed as part of these assessments. The assays will be performed at MSKCC or local CLIA-certified pathology laboratories, which have experience processing samples from patients with leukemia.

Additionally, we seek to study changes in methylation patterns with the use of this combination. This is important for understanding on-target effects as MLL-rearranged leukemia is driven by hypermethylation, and pinometostat works to inhibit DOT1L methyltransferase activity and 5-azacytidine is a DNA hypomethylating agent. The assay of choice would be an ELISA assay to quantitate the extent of H3K79 methylation in leukemia cells, performed on mandatory samples from bone marrow samples identified above. The ELISA would be performed in [name] lab at DFCI, which has extensive experience with this assay.

The ELISA would not be a CLIA-certified test and would be solely performed for research purposes as part of an integrated biomarker. Samples would be viably cryopreserved at each institution and shipped to the study coordinator MSKCC for storage. At the end of the study, the samples would be shipped to DFCI, care of [name] laboratory, and the assay would be batch run on all samples.

As the mechanism of leukemogenesis in MLL-rearranged leukemia relies on hypermethylation of H3K79 by DOT1L, leading to increased transcription of HOXA9 and Meis1, we anticipate that expression levels of these two genes will decrease with treatment. As such, we plan to use qPCR to evaluate gene expression level prior to treatment on mandatory bone marrow samples at the time points identified above. The qPCR assays will be run in the [name] lab at DFCI, which has extensive experience running these qPCR assays. This would not be a CLIA-certified

test and would be solely performed for research purposes as an integrated biomarker. Samples would be viably cryopreserved at each institution and shipped to the study coordinator MSKCC for storage. At the end of the study, the samples would be shipped to DFCI, care of [name] laboratory, and the assay would be batch run on all samples.

We anticipate that pinometostat will induce differentiation of myeloid blasts into more mature myeloid forms, based on previous research on pinometostat. As such, we will prospectively viably cryopreserve bone marrow aspirates in anticipation of flow-sorting blasts and myeloid cells. We will perform flow cytometry to assess for the upregulation of myeloid differentiation markers (such as CD11b) on each myeloid subtype, as well as perform FISH to track the compartmentalization of the MLL rearrangement. We anticipate that MLL rearrangements will be detectable in more mature myeloid cells, e.g. neutrophils, allowing us to evaluate the extent of differentiation.

We will perform these assays on selected samples. CD11B is part of the standard myeloid panel run by the CLIA-certified flow cytometry lab at MSKCC. Bone marrow samples from the above delineated timepoints will be collected and will be a mandatory part of the trial. Bone marrow aspirate samples will be centrifuged and the buffy coat will be viably cryopreserved in DMSO.

Bone marrow will be used to ensure that more blasts can be recovered and myeloid forms at different phases of maturation can be included. While we could consider assays to evaluate for synergy of these two agents, this falls outside the scope of this phase I study – we would need reference evaluations of patient treatment on each agent alone, which is not the goal of this trial. Additionally, *in vitro* assays of synergy have previously been performed in pre-clinical work. Western blots for H3K79 methylation were considered, however we would perform the ELISA first as it provides more throughput with a single assay.

This will be one of the first assessments of 5-aza-2'-deoxycytidine incorporation relative to the extent of global DNA methylation in human samples and may give further insight into the mechanism of action of azacitidine.

Correlative studies will be performed at the intervals outlined in the table so as to produce meaningful and interpretable results. As sample collection at these intervals is commonly performed as standard of care, these timepoints should be feasible for assessment.

Specimen Collection Schedule

Specimen Type	Baseline (Pre-treatment)	C1D1 prior to azacitidine, and 0.25hr, 0.5hr, and 1 hr post azacytidine treatment	C1D8	End of cycle 1	End of cycle 3	End of cycle 6 and / after cessation of therapy, whichever is first
Bone marrow	X			X	X	X
Peripheral Blood	X	X	X			

5.2 Integral Laboratory or Imaging Studies

- 5.2.1.1 11q23 rearrangement or partial tandem duplication
- 5.2.1.2 Collection of Specimen(s): Locally performed
- 5.2.1.3 Handling of Specimens(s): Locally performed
- 5.2.1.4 Shipping of Specimen(s): N/A
- 5.2.1.5 Site(s) Performing Correlative Study: Local laboratory or per local practice of using a commercial laboratory

- 5.2.1.6 Myeloid mutational panel for NPM1 and no other targetable mutations
- 5.2.1.7 Collection of Specimen(s): Locally performed
- 5.2.1.8 Handling of Specimens(s): Locally performed
- 5.2.1.9 Shipping of Specimen(s): N/A
- 5.2.1.10 Site(s) Performing Correlative Study: Local laboratory or per local practice of using a commercial laboratory

5.3 Integrated Correlative Studies

- 5.3.1.1 H3K79 ELISA
- 5.3.1.2 Collection of Specimen(s): Locally performed
- 5.3.1.3 Handling of Specimens(s): Local study coordinator
- 5.3.1.4 Shipping of Specimen(s): To [name] Lab at DFCI
- 5.3.1.5 Site(s) Performing Correlative Study: [name] Lab at DFCI

- 5.3.1.6 qPCR for HOXA9 and Meis1 Expression
- 5.3.1.7 Collection of Specimen(s): Locally performed
- 5.3.1.8 Handling of Specimens(s): Local study coordinator
- 5.3.1.9 Shipping of Specimen(s): To [name] Lab at DFCI
- 5.3.1.10 Site(s) Performing Correlative Study: [name] Lab at DFCI

- 5.3.1.11 Myeloid differentiation by Flow / FISH
- 5.3.1.12 Collection of Specimen(s): Locally performed
- 5.3.1.13 Handling of Specimens(s): Local study coordinator
- 5.3.1.14 Shipping of Specimen(s): To MSKCC
- 5.3.1.15 Site(s) Performing Correlative Study: MSKCC

- 5.3.1.16 MRD Negativity by Flow Cytometry
- 5.3.1.17 Collection of Specimen(s): Locally performed
- 5.3.1.18 Handling of Specimens(s): Local study coordinator
- 5.3.1.19 Shipping of Specimen(s): To MSKCC
- 5.3.1.20 Site(s) Performing Correlative Study: MSKCC

- 5.3.1.21 Azacitidine PK profile
- 5.3.1.22 Collection of Specimen(s): Locally performed
- 5.3.1.23 Handling of Specimens(s): Local study coordinator
- 5.3.1.24 Shipping of Specimen(s): To [name] lab at SKCCC

5.3.1.25 Site(s) Performing Correlative Study: [name] lab at SKCCC

5.4 Exploratory/Ancillary Correlative Studies

5.4.1.1 Cell storage / DNA storage

5.4.1.2 Collection of Specimen(s): Locally performed

5.4.1.3 Handling of Specimens(s): Local study coordinator

5.4.1.4 Shipping of Specimen(s): To MSKCC

5.4.1.5 Site(s) Performing Correlative Study: MSKCC

5.4.1.6 5-aza-2'-deoxycytidine Genomic Incorporation (from Azacitidine) and DNA Demethylation

5.4.1.7 Collection of Specimen(s): Locally performed

5.4.1.8 Handling of Specimens(s): Local study coordinator

5.4.1.9 Shipping of Specimen(s): To [name] lab at SKCCC

5.4.1.10 Site(s) Performing Correlative Study: [name] lab at SKCCC

5.5 Special Studies

5.5.1.1.1 N/A

6. TREATMENT PLAN

6.1 Agent Administration

Treatment will be administered on an outpatient basis. Reported adverse events and potential risks are described in Section 10. Appropriate dose modifications are described in Section 7. Hydroxyurea may be given concurrently for cytoreduction. No other investigational or commercial agents or therapies other than those described below may be administered with the intent to treat the patient's malignancy.

Dose Escalation Schedule		
Dose Level	Dose	
	Pinometostat	Azacitidine
Level -1	36 mg/m ² /day CIV infusion	75 mg/m ² /day for 7 days / cycle
Level 1*	54 mg/m ² /day CIV infusion	75 mg/m ² /day for 7 days / cycle
Level 2	90 mg/m ² /day CIV infusion	75 mg/m ² /day for 7 days / cycle

*Starting dose levels

Regimen Description					
Agent	Premedications; Precautions	Dose	Route	Schedule	Cycle Length
Pinometostat	None	** in NS to a final concentration between 0.54 mg/ml and 5.63 mg/ml	Continuous IV infusion	Days 1-28	28 days (4 weeks)
Azacitidine	Consider antiemetic premedication as per local institutional practices, e.g. 8mg ondansetron 60min prior to administration	75 mg/m ² /day	IV or SC, as per local institutional preference; given daily for 7 of the first 10 days of each cycle, e.g. given for 5 days, 2-day break, and given for an additional 2 days	Given for 7 of the first 10 days of each cycle	

**Doses as appropriate for assigned dose level.

6.1.1 CTEP IND Agent: Pinometostat

Pinometostat is given as IV continuous infusion administered at a constant flow rate. Pinometostat must be diluted in 0.9% sodium chloride to a final concentration between 0.54 mg/ml and 5.63 mg/ml prior to administration.

Patients should have a peripherally inserted central catheter (PICC) or similar central venous access device with a dedicated lumen for pinometostat alone.

Pinometostat will be administered as a continuous IV infusion through the dedicated lumen of the central venous access device. The patient will return to the study center approximately every 72 hours to have the infusion medication refilled. The use of pumps to administer the medication should follow manufacturer's and institutional guidelines. The patient or caregiver should be trained on how to use the pump or other device used to administer the medication. The patient or caregiver should also be trained on signs that may indicate that there is an issue with drug delivery.

Refer to section 8.1 for compatible IV infusion bags and sets.

The starting dose of pinometostat in the phase 1b will be 54 mg/m²/day (actual body surface area (BSA)). BSA is calculated as per institutional policy; alternatively, the Du Bois Method (Arch Intern Med. 1916; 17:863-871) may be used.

BSA should be calculated prior to each cycle. The administered dose should be adjusted if the patient's weight changes $\geq 10\%$ from baseline and may be rounded to the nearest mg.

6.1.2 Other Agent(s)

Prophylactic antiemetics can be given prior to azacitidine administration as per local institutional practices. One example of this would be the administration of 8mg ondansetron 60 min prior to azacitidine administration.

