- 3.2.7 Pregnant women are excluded from this study because pinometostat is an agent with the potential for teratogenic or abortifacient effects. Because there is an unknown but potential risk for adverse events in nursing infants secondary to treatment of the mother with pinometostat, breastfeeding should be discontinued if the mother is treated with pinometostat. These potential risks may also apply to other agents used in this study.
- 3.2.8 HIV-positive patients on combination antiretroviral therapy should have their regimen reviewed for potential pharmacokinetic interactions with pinometostat and azacitidine. In the event of a potential interaction, alternative therapies may be considered in consultation with the patient's primary HIV physician.
- 3.2.9 Absence of an 11q23 rearrangement or absence of an 11q23 partial tandem duplication
- 3.2.10 Patients with an active bleeding diathesis.
- 3.2.11 Patients at increased risk of QT prolongation (e.g. from known long-QT syndrome) or who have a corrected QT interval that is persistently longer than 450ms despite adjustments to other medications
- 3.2.12 Patients who are eligible for or willing to receive intensive induction therapy for de novo AML

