7.1 Guidelines for Management of QT Prolongation

The discussion of the emergency management of torsade de pointes and its hemodynamic consequences is beyond the scope of this guideline.

Both nonclinical and clinical data provided suggest a risk of QT prolongation with pinometostat, and the risk may be additive in combination with azacitidine. As such, a baseline EKG should be performed to evaluate for QT prolongation. A weekly EKG should be performed during cycle 1 to monitor for QT prolongation.

Subjects may be at increased risk for the development of QT prolongation when treated with pinometostat and azacitidine in combination with fluoroquinolones, azole antifungal agents or serotonin (5-HT₃) antagonists. Investigators need to be vigilant; refrain from administering concomitant medications associated with QT prolongation and if no other therapeutic options are available, monitor subjects receiving pinometostat and azacitidine with the combination of these drugs, and evaluate EKG and electrolytes (including potassium, magnesium, and calcium) particularly in subjects presenting with nausea, vomiting or diarrhea.

Subjects who experience prolongation of the QTc interval using Fridericia's equation (QTcF) interval to > 480 msec (CTCAE Grade ≥ 2) while treated with pinometostat and azacitidine should be promptly evaluated for causality of the QTcF prolongation and managed according to the following guidelines:

- Levels of electrolytes (potassium, calcium and magnesium) should be checked and supplementation given to correct any values outside the normal range.
- Concomitant therapies should be reviewed and adjusted as appropriate for medication with known QT prolonging effects.
- If no other cause is identified and the Investigator believes it is appropriate, particularly if QTcF remains elevated (after above measures have been implemented, or as determined by the Investigator), study drug may be interrupted, and an EKG should be rechecked in approximately 1 week after the QTcF prolongation was first observed or more frequently as clinically indicated. If QTcF has recovered or improved and the Investigator believes it is safe to do so, re-challenge with pinometostat should be considered if held.
- EKGs should be conducted at least weekly (e.g., at every scheduled visit) for 2 weeks following QTcF reduction ≤ 480 msec.

Grade 2 (QTcF > 480 and ≤ 500 msec)

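### Sections 6.1 and 6.1.2 offer ondansetron as the only premedication example, without the QT condition that Section 7.1 places on its drug class

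*Combined protocol and SAP*

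**What the plan says.** In the Section 6.1 regimen table, the column for premedications and precautions invites sites to consider an antiemetic before azacitidine according to local practice, "e.g. 8mg ondansetron 60min prior to administration". Section 6.1.2 repeats the suggestion: "One example of this would be the administration of 8mg ondansetron 60 min prior to azacitidine administration". No other agent is named in either place. The one pointer from 6.1 to Section 7 is "Appropriate dose modifications are described in Section 7".

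Section 7.1 states that pinometostat carries a QT risk which may be additive with azacitidine. It says the risk may rise "when treated with pinometostat and azacitidine in combination with fluoroquinolones, azole antifungal agents or serotonin"; the sentence goes on to specify 5-HT3 antagonists. Investigators are told to "refrain from administering concomitant medications associated with QT prolongation and if no other therapeutic options are available, monitor subjects" on such combinations, and to "evaluate EKG and electrolytes (including potassium, magnesium, and calcium) particularly in subjects presenting with nausea, vomiting or diarrhea". For scheduled monitoring it asks for a baseline EKG and adds: "A weekly EKG should be performed during cycle 1 to monitor for QT prolongation".

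**The concern.** A site building its azacitidine orders will read the regimen table and 6.1.2. Both show a drug from a class that 7.1 treats as a fallback, and the table shows it in the very column meant for precautions. A site that adopts the example as routine first-line premedication, without considering alternatives or doing the EKG and electrolyte check, would depart from 7.1 without any prompt that it was doing so.

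What is at stake is patient safety and clear instruction to sites. QT prolongation is on the pinometostat risk list in Section 10.1.1.1. No sample size, error rate or endpoint is affected.

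**Working it through.** This is a comparison of texts plus a count of calendar marks. The plan gives no figure to reproduce.

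1. **Is premedication required?** No. Both places are permissive and defer to local practice.
2. **Is ondansetron covered by 7.1?** The documents do not print its class. That it is a 5-HT3 antagonist is standard nomenclature, and 7.1 names the class.
3. **What does 7.1 require?** First refrain; if no other option exists, use with monitoring. This is a conditional default with no cycle limit.
4. **Does the printed example meet the condition?** Not on its face. Section 6.4 permits intermittent dexamethasone 10 mg as an antiemetic, so the protocol itself contemplates another agent. The condition could still be met for a particular patient.
5. **Do the exposures overlap?** Yes. Section 6.1 runs pinometostat on days 1–28 and gives azacitidine on 7 of the first 10 days, so on the planned schedule every premedication day falls within the infusion.
6. **What does the Section 11 calendar schedule?**

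| | Cycle 1 | Cycles 2–6 |
|---|---|---|
| Possible premedication days | 7 × 1 = 7 | 7 × 5 = 35 |
| EKG marks | 4 (day 1, day 8, weeks 3 and 4), plus 1 pre-study | 0 |
| Day-1 chemistry marks | 1 of 1 | 5 of 5 |

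The total is 7 + 35 = 42 possible premedication days. This is an upper bound that assumes every azacitidine dose is premedicated and all 6 cycles are given. The chemistry panel includes potassium, magnesium and calcium, so the scheduled gap concerns the EKG and not electrolytes. Patients who continue beyond 6 months follow the cycle 2 schedule, which also has no EKG mark. The EKG row is labelled as indicated in both calendar tables.

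**The case against.** The strongest reply is that nothing is missing from the safety rule. Section 7.1 binds in every cycle, 6.1 and 6.1.2 neither direct ondansetron use nor waive 7.1, and a site can comply with all three. Other safeguards also exist. Section 3.2.11 excludes patients at increased QT risk or with a persistently long corrected QT. Section 6.1 refers to Section 10, where QT prolongation is listed. Section 6.4 requires all concurrent drugs to be recorded and a current reference to be consulted, although its stated concern is interactions. All of this stands and limits the point to a minor one. It does not reconcile the example with the default in 7.1.

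Three stronger readings are tempting, and the documents do not support them.

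- A reader might infer that the protocol tells sites to give a prohibited drug. It does not: premedication is optional and 7.1 is not a ban.
- A reader might infer from the table that 35 of 42 premedication days are unmonitored. That ratio is simply 5 of 6 cycles. It describes fixed scheduling, not harm: use of a 5-HT3 antagonist is itself a reason for an EKG under 7.1, and the as-indicated label allows for it.
- A reader might infer that dose-limiting toxicity counts are compromised. Section 7 does exclude only events incontrovertibly due to another cause, so a Grade 3 QT event in a patient given ondansetron might be counted. With no event rate in the documents, no effect on the dose decision can be shown.

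**Conclusion.** The inconsistency is real but minor. The only example in 6.1 and 6.1.2 belongs to a class that 7.1 says to avoid by default, and neither the condition nor the monitoring is carried over. After cycle 1 no EKG is fixed in the calendar, so the check depends on the site linking its premedication to 7.1, and the premedication text does not make that link. The comparison of texts is firm and rests on one fact from outside the documents, ondansetron's drug class. The safety consequence is conditional on a site following the example without applying 7.1, and its size cannot be estimated.

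**What to change.** In both the 6.1 regimen table and 6.1.2, drop ondansetron as the unqualified example and state:

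> Antiemetic premedication per local practice, subject to Section 7.1: refrain from 5-HT3 antagonists and other QT-prolonging antiemetics unless no other therapeutic option is available. If one is used, evaluate EKG and electrolytes (potassium, magnesium, calcium) as in 7.1 in each cycle of use, including after cycle 1.

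This keeps 7.1's threshold; a softer preference for other agents would put a second, looser standard beside it. Dexamethasone should not be named as the routine replacement. Section 6.4 permits intermittent use but discourages chronic steroids, and 7.3 uses dexamethasone to treat differentiation syndrome.

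The cost is wording in two places and occasional EKGs that 7.1 already calls for. The real downside is a narrower antiemetic choice and possibly poorer control of emesis. That matters because 7.1 asks for particular attention to EKG and electrolytes in patients with nausea, vomiting or diarrhea, so the wording leaves 5-HT3 antagonists available when nothing else will do.
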